## 2.0 Background

### 2.1 Scientific Background and Gaps

Overweight and obesity are America's number one health concern. The prevalence of obesity in the US is greater than 36%, which is far above the Healthy People 2020 objective of less than 30.5%. Perhaps most concerning is the rate that obesity has increased, having doubled since 1970. As the second most preventable cause of death, obesity is a risk factor for diabetes, cardiovascular disease, stroke, and cancer, all major causes of death in the US. Addressing obesity through lifestyle interventions decreases the risk of developing type 2 diabetes, a disease which affects over 29 million people (9.3% of the US population). Diabetes is associated with serious complications, including cardiovascular disease, blindness, renal failure and lower extremity amputation. Although complications are preventable with proper medical and lifestyle management, including weight loss, nearly half of patients with diabetes do not have adequate glycemic control.

Primary care clinics may be an ideal setting for weight control interventions. Greater than 80% of Americans see a PCP regularly and access to primary care is expected to increase with health care reform. Further, as PCPs identify and treat the multitude of conditions affected by being overweight, including diabetes, they are ideally positioned to best engage their patients in weight management. The Centers for Medicare and Medicaid Services (CMS) implemented a healthcare procedure coding system code for intensive behavioral therapy (IBT) for obesity within primary care settings in 2012 to facilitate payment for addressing obesity, which was followed by universal coverage by insurers for IBT for adults of all ages in 2013. However, the impact of this coverage on patient-centered outcomes is largely unknown.

The proposed work leverages the novel infrastructure of the Patient-Centered Outcomes Research Institute-funded PaTH Clinical Data Research Network (CDRN), a partnership of four Mid-Atlantic academic health systems (Penn State Hershey Medical Center, University of Pittsburgh Medical Center, Temple Health System, and Johns Hopkins Health System) that have established governance to operate as an integrated research network. In 2015, the University of Utah and Geisinger Health System also joined PaTH, creating an electronic health record (EHR)-based data infrastructure across three states (Maryland, Pennsylvania, and Utah).

[figure not shown]
We have additionally added a focus on rural/urban differences in provision of obesity screening and counseling and the resultant impact on weight loss and diabetes incidence. Rural populations have a 17% higher prevalence of diabetes when compared to their urban counterparts. As a result, diabetes is the second highest priority for Rural Healthy People 2020. Additionally, rural populations have lower rates of guideline-concordant diabetes services, although this has been inadequately investigated. Studies report adults with diabetes living in rural communities are less likely to receive adequate diabetes-related care than non-rural residents, but are limited in study design (i.e., reliant on patient self-report or medical expenditure data). We propose leveraging the novel infrastructure of the Patient-Centered Outcomes Research Institute-funded PaTH CDRN to understand the rural and urban effects on diabetes and its complications. The integration of six large health institutions spanning a diversity of rural and urban populations has the unique opportunity to overcome limitations of prior studies by using health record data. In this way, our proposed study will address important gaps in our understanding of rural/urban differences in diabetes outcomes and guide future approaches to address and eliminate disparities.

Utilizing the PaTH CDRN offers an opportunity to study rural/urban effects, given that the 6 health institution network (University of Pittsburgh Medical Center, Penn State Hershey Medical Center, Temple Health System, Johns Hopkins Health System, University of Utah Health Care, and Geisinger Health System) covers significant populations in both rural and urban counties. For example, PaTH CDRN's service area includes more than 85% of the population of Pennsylvania, including coverage in nearly every one of Pennsylvania's 67 counties (48 rural and 19 urban, see map below). Further, 27% of Pennsylvania's residents live in rural counties, which is higher than the national average of 20%, offering opportunity to better understand diabetes care in this setting. The addition of the University of Utah also offers a different geographic location with similar opportunities to study rural/urban effects. This system provides care for Utahns and residents of five surrounding states in a referral area encompassing more than 10% of the continental US, the vast majority of which is rural. Johns Hopkins Health System, Temple Health System, and the University of Pittsburgh Medical Center offer three different urban populations for comparison.

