## 2.2 Previous Data

### *Preliminary Studies*

PaTH Clinical Data Research Network

**Overview.** The PaTH Clinical Data Research Network (CDRN) brings together four Mid-Atlantic academic health systems—the University of Pittsburgh/University of Pittsburgh Medical Center (UPMC), Penn State College of Medicine/Hershey Medical Center, Temple University School of Medicine/Temple Health, and the Johns Hopkins University/Johns Hopkins Health System/Johns Hopkins Health Care to function as an integrated research network and learning health system, providing an infrastructure for pragmatic clinical trials and observational studies that require populations beyond a single health system to answer important patient-centered clinical and health services questions ([www.pathnetwork.org](http://www.pathnetwork.org)). Funded by the Patient-Centered Outcomes Research Institute (PCORI) in March 2014, the PaTH CDRN is one of 11 CDRNs across the country. Along with 18 Patient-Powered Research Networks (PPRNs), these 11 CDRNs form PCORnet—the National Patient-Centered Clinical Research Network—a national network for conducting clinical outcomes research ([www.pcornet.org](http://www.pcornet.org)). The goal of PCORnet is to improve the nation’s capacity to conduct comparative effectiveness research by creating large, highly representative network from which to draw data, while protecting patient privacy and ensuring data security.

PaTH’s mission during its initial funding period is to create the technical, governance, and patient- and clinician-engagement infrastructure to conduct clinical and health services research across diverse health systems. For this proposal, we will include all four of the PaTH institutions (Pittsburgh, Penn State, Johns Hopkins, and Temple), thus representing patients from Pennsylvania and Maryland. The University of Utah will join the PaTH network in 2015, which is an exciting new partnership for our network (see Table 3). The addition of the University of Utah greatly strengthens the proposed project by adding a state that has not adopted Medicaid expansion.

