In the multi-level modeling, the first-level unit is the yearly measurement for the individual subject (pre- and post-policy), the second-level unit is the individual subject, the third-level unit is the health system or clinic within the health system (cluster), and the fourth-level unit is the state. We set year 2014 as time origin for Utah when considering the policy impact of the ACA. Let  $Y_{ijkt}$  denote the binary response of having controlled diabetes at year  $t$  since policy changes for the  $k^{\text{th}}$  subject within the  $j^{\text{th}}$  cluster of the  $i^{\text{th}}$  state,  $t = -5, -4, \dots, 0, 1, \dots, 5$ ,  $i = 1, 2, 3$ ;  $j = 1, 2, \dots, c_i$ , and  $k = 1, 2, \dots, n_{ij}$ , where  $c_i$  is the number of clusters within the  $i^{\text{th}}$  state and  $n_{ij}$  is the sample size within the  $j^{\text{th}}$  cluster of the  $i^{\text{th}}$  state. An individual subject may not be in the system for all 11 timepoints of measurement, so  $t$  will have a smaller range of values for that individual subject. Also due to the different timeline of policy changes, the number of years before and after policy changes may vary. The probability of having controlled diabetes,  $\mu_{ijkt} = E(Y_{ijkt}) = \Pr[Y_{ijkt} = 1]$ , can be described by the following segmented logistic regression model

$$\begin{aligned} \text{logit } \mu_{ijkt} &= \log \{\Pr[Y_{ijkt} = 1] / \Pr[Y_{ijkt} = 0]\} \\ &= \beta_{0ijk} + (t + 5) \beta_{1ijk} && \text{if } -5 \leq t \leq 0, \text{ pre-period before policy changes} \\ &= \beta_{0ijk} + 5 \beta_{1ijk} + t \beta_{2ijk} && \text{if } 0 \leq t \leq 5, \text{ post-period after policy changes} \end{aligned}$$

where  $\beta_{mijk}$  ( $m = 0, 1, 2$ ) are subject-specific regression parameters, with  $\beta_{0ijk}$  being the log odds of having controlled diabetes at  $t = -5$ , and  $\beta_{1ijk}$  and  $\beta_{2ijk}$  being the slopes (annual change in log odds) for the pre- and post-periods, respectively. In the framework of a mixed-effects model, each  $\beta_{mijk}$  is modeled by

$$\beta_{mijk} = \mathbf{x}_{mijk}^T \boldsymbol{\beta}_m + \mathbf{z}_{ij}^T \boldsymbol{\gamma}_{1ij} + \boldsymbol{\gamma}_{2mijk}$$

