where  $\mathbf{x}_{mijk}$  is the vector of regressors for the fixed effects,  $\boldsymbol{\beta}_m$  is the corresponding vector of fixed-effects parameter coefficients,  $\mathbf{z}_{ij}$  is a vector of cluster-level regressors for the random effects for the  $j^{\text{th}}$  cluster of the  $i^{\text{th}}$  state,  $\boldsymbol{\gamma}_{1ij}$  is the cluster-level random-effect coefficients and is common to all  $m$ , and  $\boldsymbol{\gamma}_{2mijk}$  is the subject-level random-effect coefficients associated with the parameter  $\beta_m$  for the  $k^{\text{th}}$  subject within the  $j^{\text{th}}$  cluster. The random effects are assumed to follow a multivariate normal distribution with mean zero. Because the vector  $\mathbf{x}_{mijk}$  may include subject-level, cluster-level and state-level exposure variables, the fixed effects parameter vectors  $\boldsymbol{\beta}_1$  and  $\boldsymbol{\beta}_2$  represent the effects of different exposure variables on the annual changes in the pre- and post-periods. Thus, we may perform statistical tests to examine whether there are differences in trends between the pre- and post-periods overall and for each state, and whether the patterns of changes differ between the states.

Similarly for a count outcome  $Y_{ijkt}$  (e.g., number of clinical visits), we define the expected value  $\mu_{ijkt} = E(Y_{ijkt})$  and apply a Poisson regression model based on the natural log link function. The log expected number of clinical visits,  $\log(\mu_{ijkt})$ , can be modeled with the aforementioned segmented mixed-effects model. The use of an offset term in the models yields the estimates of the rate of clinical visits rather than the mean number of visits. The fixed-effect parameters,  $\beta_1$  and  $\beta_2$ , represent the effects of exposure variables on the annual changes in log of incidence rates for the pre- and post-periods, respectively. For a continuous outcome  $Y_{ijkt}$ , we will model the mean,  $\mu_{ijkt} = E(Y_{ijkt})$ , with the mixed-effects model and the parameters  $\beta_1$  and  $\beta_2$  indicate the effects of exposure variables on the annual changes in the outcomes for the pre- and post-periods, respectively. All final statistical models will be assessed with respect to the goodness-of-fit and the appropriateness of model assumptions. Statistical software SAS 9.4 and R environment will be used to implement the proposed analyses.

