### **9.1 Confidentiality**

#### **9.1.1 Identifiers associated with data and/or specimens**

- Names;
- All geographical subdivisions smaller than a State, including street address, city, county, precinct, zip code, and their equivalent geocodes;
- Birth date, admission date, discharge date, date of death;
- Phone numbers;
- Fax numbers;
- Electronic mail addresses;
- Social Security numbers;
- Medical record numbers;
- Health plan beneficiary numbers;
- Account numbers;
- Certificate/license numbers;
- Vehicle identifiers and serial numbers, including license plate numbers;
- Device identifiers and serial numbers;
- Web Universal Resource Locators (URLs);
- Internet Protocol (IP) address numbers;
- Biometric identifiers, including finger and voice prints;
- Full face photographic images and any comparable images (including videos);
- Any other unique identifying number, characteristic, or code (note this does not mean the unique code assigned by the investigator to code the data);
- Other (please specify):

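### The model indexes every Utah-system patient to Utah, although that system also serves five other states; this may misclassify policy exposure in the ACA/Medicaid-expansion and between-state contrasts only

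*Combined protocol and SAP*

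**What the plan says.** Section 8.0 sets out four levels: yearly measurement, subject, cluster and state. It says that "the third-level unit is the health system or clinic within the health system (cluster), and the fourth-level unit is the state". The state index takes three values, and each state has its own number of clusters. Section 2.1 names the states when it describes a "data infrastructure across three states (Maryland, Pennsylvania, and Utah").

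The same section describes the Utah catchment: "This system provides care for Utahns and residents of five surrounding states", with a referral area put at over 10% of the continental US. The documents do not name the five states, give their Medicaid policy, or say what share of Utah-system patients live in them.

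State policy enters in four places:
- Section 2.2 (Preliminary Studies) values Utah for "adding a state that has not adopted Medicaid expansion".
- The cohort definitions in Section 7.2 name Pennsylvania's Medicaid expansion as the last policy change under study.
- Section 8.0 states: "We set year 2014 as time origin for Utah when considering the policy impact of the ACA".
- Section 8.0 also foresees tests of trend within each state and of "whether the patterns of changes differ between the states".

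No section says how to classify a patient who lives in a state other than these three.

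**The concern.** Take Medicaid eligibility to follow the state in which a person lives; this is an assumption, as the documents do not discuss it. A resident of a neighbouring state who uses the Utah system then carries Utah's non-expansion status in the model, whatever that person's own state did. The Utah group would be a mixture of policy environments, and a contrast between it and the expansion states would be pulled toward zero.

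This would be a bias, so the large samples on which the Statistical Power paragraph relies would not remove it. They would only estimate the mixed contrast more precisely.

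**Working it through.** **Step 1. Where the model puts an out-of-state patient.** The Utah system serves 1 + 5 = 6 states (Section 2.1). If the state index meant residence, it would need at least 6 values for Utah and its five neighbours, plus 2 for Maryland and Pennsylvania, so 8. It has 3. A health system that draws on six states also could not be nested in one of them. No sentence says outright that state means the location of the system, but the index range and the nesting leave no other place for these patients.

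**Step 2. Which analyses depend on the state index.**
- Counseling-coverage aims (Section 1.0): Section 2.1 dates the coverage to 2012 for CMS and 2013 for all insurers, without regard to state. Not exposed.
- County rural/urban analysis (Section 8.0, population-level analyses): it starts time at the beginning of the study period and uses no policy date. Not exposed.
- ACA/Medicaid-expansion contrast and between-state tests (Sections 2.2, 7.2 and 8.0): exposed.

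**Step 3. The plan's own figures.** The plan gives no power, effect size or sample size for the between-state comparison, so there is no design figure to reproduce. The counts and time points in Sections 7.2 and 8.0 can be checked:
- Diabetes: 25,219 + 150,589 + 60,324 + 40,536 + 51,787 = 328,455, as stated. Utah share: 51,787 / 328,455 = 15.8%.
- At risk: 167,799 + 950,020 + 471,860 + 212,314 + 260,506 = 2,062,499, as stated. Utah share: 260,506 / 2,062,499 = 12.6%.
- With a 2014 origin, 2009 to 2019 gives t = -5 to 5, which is 11 points, as in Section 8.0.

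**Step 4. Effect on the contrast.** Let D be the effect of expansion on those exposed to it, with the same size and timing for all. Let f be the share of Utah-system patients who live elsewhere, and g the share of those who live under expansion. Treat patients of the other systems as correctly classified. The expansion group changes by D and the Utah group by f × g × D, so the observed contrast is D × (1 - f × g). Both f and g are assumptions. The share of the contrast retained is:

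| f | g = 0 | g = 0.5 | g = 1 |
|---|---|---|---|
| 2% | 1.00 | 0.99 | 0.98 |
| 5% | 1.00 | 0.975 | 0.95 |
| 10% | 1.00 | 0.95 | 0.90 |
| 20% | 1.00 | 0.90 | 0.80 |
| 30% | 1.00 | 0.85 | 0.70 |

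**Step 5. Number of patients.**
- Diabetes: 0.05 × 51,787 = 2,589; 0.20 × 51,787 = 10,357.
- At risk: 0.05 × 260,506 = 13,025; 0.20 × 260,506 = 52,101.

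These bases are network counts by diagnosis or BMI, taken before the cohorts are limited to patients with two primary care visits or claims data. The analysed numbers would be smaller for the same f.

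**Step 6. The group most likely to matter.** If expansion acts mainly through Medicaid and uninsured patients, the relevant Utah diabetes patients number 4,189 + 2,337 = 6,526, or 6,526 / 51,787 = 12.6%. The value of f within that group then matters more than f overall. Neither is given.

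**The case against.** The strongest reply is that the written model can hold a residence-based exposure. Section 8.0 allows regressors at subject, cluster and state level, Section 7.2 lists insurance status as an individual-level variable, and the subgroup analyses separate patients by when they held insurance. All this can follow a patient's coverage wherever the patient lives. It stands as far as it goes: the model could be fitted correctly. But no residence variable is named, and a general allowance for regressors does not change the state index or supply a rule for out-of-state patients.

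A reader might infer that the Utah comparison is diluted as a matter of fact. The documents do not support that. Dilution needs some of the five states to have had a different policy, and their policies are not given. If none differed, g = 0 and nothing is lost.

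A reader might also infer that 2014 is the wrong time origin for these patients. That is not shown either. Section 2.2 calls Utah a non-expansion state, so 2014 is a reference year for the ACA analysis and not a Utah expansion date. Nothing shows that another date applies to its neighbours' residents.

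Two further points limit the weight of the concern. The referral area describes the whole system, and the rule of two primary care visits probably lowers f, although entry through claims data has no such limit. The between-state tests are also worded as something the analysts may do, and Section 2.1 values Utah for its rural population as well.

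**Conclusion.** The gap is real but narrow. As written, out-of-state patients of the Utah system can only be indexed to Utah, and their policy exposure may be wrong in the ACA/Medicaid-expansion and between-state contrasts. The stated aims on counseling coverage and the county rural/urban analysis are untouched.

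The size cannot be fixed from the documents. Each 5 percentage points of out-of-state patients removes at most 5% of the contrast, and removes nothing if their states had Utah's policy. This rests on three assumptions: Medicaid access follows residence, the expansion effect has the same size and timing in everyone exposed, and patients elsewhere in the network are correctly classified. The change is worth making because it is cheap and because the reported out-of-state count would show how large f is.

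**What to change.** For the ACA/Medicaid-expansion and between-state contrasts, define state policy exposure by the patient's state of residence. Baseline or most recent residence is enough if yearly history is not held. Alternatively, limit these contrasts to residents of Maryland, Pennsylvania and Utah. In either case keep the health system or clinic as the cluster, and report how many patients live outside the three states. The other analyses need no change.

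The cost is a few sentences in Section 8.0, one field in the extract, and a slightly smaller Utah group in these contrasts if out-of-state patients are left out. The field should be specified before extraction, because sites remove identifying information before transfer. State is coarser than anything covered by the geographic item in Section 9.1.1 ("All geographical subdivisions smaller than a State"), and coarser than the county-level data already planned in Section 8.0. The documents do not show whether the field is already held in the extract, so the sites should confirm this.

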## 2.2 Previous Data

### *Preliminary Studies*

PaTH Clinical Data Research Network

**Overview.** The PaTH Clinical Data Research Network (CDRN) brings together four Mid-Atlantic academic health systems—the University of Pittsburgh/University of Pittsburgh Medical Center (UPMC), Penn State College of Medicine/Hershey Medical Center, Temple University School of Medicine/Temple Health, and the Johns Hopkins University/Johns Hopkins Health System/Johns Hopkins Health Care to function as an integrated research network and learning health system, providing an infrastructure for pragmatic clinical trials and observational studies that require populations beyond a single health system to answer important patient-centered clinical and health services questions ([www.pathnetwork.org](http://www.pathnetwork.org)). Funded by the Patient-Centered Outcomes Research Institute (PCORI) in March 2014, the PaTH CDRN is one of 11 CDRNs across the country. Along with 18 Patient-Powered Research Networks (PPRNs), these 11 CDRNs form PCORnet—the National Patient-Centered Clinical Research Network—a national network for conducting clinical outcomes research ([www.pcornet.org](http://www.pcornet.org)). The goal of PCORnet is to improve the nation’s capacity to conduct comparative effectiveness research by creating large, highly representative network from which to draw data, while protecting patient privacy and ensuring data security.

PaTH’s mission during its initial funding period is to create the technical, governance, and patient- and clinician-engagement infrastructure to conduct clinical and health services research across diverse health systems. For this proposal, we will include all four of the PaTH institutions (Pittsburgh, Penn State, Johns Hopkins, and Temple), thus representing patients from Pennsylvania and Maryland. The University of Utah will join the PaTH network in 2015, which is an exciting new partnership for our network (see Table 3). The addition of the University of Utah greatly strengthens the proposed project by adding a state that has not adopted Medicaid expansion.

The University of Pittsburgh is the lead site for the PaTH Network, with [name], MS as the PaTH Network PI. The overall operations of the PaTH Network are run by the PaTH Steering under [name] lead. [name] and the PaTH Steering Committee enthusiastically support this Penn State application to RFA-DP-15-001 (see [name] letter of support), which will leverage the data infrastructure, established governance and regulatory policies related to data security, data sharing and human subjects protection of the PaTH Network.

